6.1 Screening and Consenting (D-60 to D-32)

6.1.1 Potential participants interested in the study will respond to study ads. Recruiters from the Hope Clinic will then contact them for a telephone screening, during which the research study will be explained in lay terms and eligibility criteria will be reviewed. If all eligibility criteria are met and the participant remains interested, an in-person screening appointment will be scheduled. Prior participants in other studies conducted at the Hope Clinic, and who had indicated their willingness to participate in other studies may also be contacted for a telephone screening visit.

6.1.2 At the in-person screening appointment , study staff will review the informed consent form with the participant and will answer all questions related to the study. Once the participant signs the informed consent, they will be assigned a unique study participation number. The following procedures will be performed:

- Recording of demographic information and review of medical history including recent influenza infection, including current medication use (medications that may interact with Atorvastatin) and vaccination history (previous receipt of influenza vaccines).
- Vital signs and targeted physical exam as indicated based on review of participant health status.
- A urine pregnancy test will be performed if the participant is a woman of child-bearing potential.
- Blood sample collection for baseline immunological assays and baseline clinical labs. Clinical labs may be repeated at investigator discretion.

6.1.3 Participants who remain eligible for the study will be randomized to either Statin therapy + QIV arm or QIV alone arm. Participants randomized to the Statin therapy+ QIV arm will receive the Atorvastatin pills with clear instructions on how to use them in a separate visit.

6.1.4 Clinical staff wil provide participants with a stool collection kit along with an information sheet explaining how the stool collection is done. The steps will be explained to the participant who will be asked to provide a stool sample on D-31, D1, and D29.

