2. History of a medical condition resulting in impaired immunity such as active solid tumors, leukemia, lymphoma, use of immunosuppressive drugs, chemotherapy or radiation therapy. Persons with previous skin cancers or cured non-lymphatic tumors are not excluded from the study.
3. History of HIV, Hepatitis B or Hepatitis C infection.
4. Chronic clinically significant medical problems that could be considered active or unstable (i.e diagnosed within the past 3 months or requiring a change in medication within the past 3 months). This is including (but not limited to):
 - a. Insulin dependent diabetes

- b. Severe heart disease (including arrhythmias)
- c. Severe lung disease
- d. Severe liver disease
- e. Severe kidney disease
- f. Severe hypertension: defined as life-threatening consequences (e.g., malignant hypertension, transient or permanent neurologic deficit).
- 5. BMI > 30
- 6. Current or previous use of statins or any other lipid-lowering drug.
- 7. Pregnancy or breast feeding, or plans to become pregnant in the first 3 months of study participation.
- 8. History of influenza infection within the same influenza season.
- 9. Receipt of blood products or immune globulin product within the prior 3 months.
- 10. History of excessive alcohol consumption, drug use, psychiatric conditions, social conditions or occupational conditions that in the opinion of the investigator would preclude compliance with the trial.
- 11. Receipt of any live vaccines 30 days before, or plans to receive any live vaccines 30 days after vaccination.
- 12. Receipt of any inactivated vaccines 14 days before, or plans to receive any inactivated vaccines 14 days after vaccination.

For participants randomized to the statin therapy+QIV group:

- 1. Participant is currently taking any medication that has known interactions with statin therapy.
- 2. History of renal or hepatic impairment.
- 3. Safety lab results showing:
 - a. CPK \geq 1.5 ULN
 - b. AST \geq 1.5 ULN
 - c. ALT \geq 1.5 ULN
 - d. LDL \geq 160 mg/dL

12. Population

HMG-CoA reductase inhibitors decrease cholesterol synthesis and possibly the synthesis of other biologically active substances derived from cholesterol. This may cause fetal harm when administered to pregnant female. Pregnant women are also excluded from the study as their immune responses after vaccination will differ from the general population.

13. Vulnerable Populations

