18.1 Risks of Investigational Products/Interventions

Atorvastatin therapy

Atorvastatin is an FDA-approved lipid lowering drug that is widely used. In some cases, this statin may be associated with the following risks:

- Diarrhea, nasopharyngitis, arthralgia in 4-14%

- Insomnia in 3%
- Nausea and dyspepsia in 4-6%
- Increased transaminases in 2-3%
- Muscle spasms, myalgia, musculoskeletal pain in 3 to 8%

Treatment with Atorvastatin may also be rarely linked to more serious risks such as:

- Hypersensitivity or severe allergic reaction including anaphylaxis, angioneurotic edema, erythema multiforme, Stevens-Johnson syndrome, and toxic epidermal necrolysis
- Acute liver failure or decompensated cirrhosis
- Nonserious and reversible cognitive side effects
- Fatal and nonfatal hepatic failure
- Increases in HbA1c and fasting serum glucose levels
- Myopathy and rhabdomyolysis: risk increased with renal impairment, age>65 and hypothyroidism
- Increases in serum transaminases. These changes occurred following the start of statin therapy, were not accompanied by other symptoms, and reversible after drug discontinuation
- Persistent increases to more than three times the ULN in serum transaminases have occurred in approximately 0.7% of patients
- Immune-mediated necrotizing myopathy: characterized by muscle biopsy showing necrotizing myopathy without significant inflammation, improvement with immunosuppressive agents, proximal muscle weakness, and elevated serum creatine kinase, which persist despite discontinuation of statin treatment

A scientific statement from the American Heart Association²² supports the safety of statin therapy including in people at low risk for cardiovascular disease, noting the risk of statin-induced serious muscle injury is <0.1% and risk of serious hepatotoxicity is <0.01%. Current product labels do not include the need for routine monitoring of liver enzymes if these are normal prior to initiating statin therapy. For safety, liver enzymes and creatine phosphokinase (CPK) will be monitored on a regular basis during the study.

Seasonal influenza vaccine

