22.4 Stopping Rules

Study Stopping Rules:

Study procedures will be suspended pending expedited review of all pertinent data by the institutional review board and the ISM if Atorvastatin or QIV were recalled by the manufacturer.

Also, procedures will be suspended pending review of all pertinent data by the ISM after the occurrence of any of the following:

- 1 case of statin-induced necrotizing autoimmune myopathy
- 1 case of acute liver injury
- 2 cases of severe myalgia

Individual participant Stopping Rules:

Early study termination will occur in participants due to any of the following circumstances detailed in Section 16.

Conditions for continuation of treatment or early termination of treatment/Follow-up:

Please refer to Section 17.

Follow-up After Early Study Termination:

Participants who are prematurely terminated from the study due to an AE will be followed until resolution of the AE or until 28 days after a participant terminates from the study. Resolution of an AE is defined as the return to baseline status or as stabilization of the condition with the expectation that it will remain chronic.

After assessing terminated participants for safety under the provisions stated above, the subject will be seen in clinic, if necessary.

Participant Replacement

In the case of premature termination (Day 8 or earlier), extra participants may be recruited, at the discretion of the Principal Investigator, to maintain the target sample size.

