Appendix A. Schedule of Procedures

	-60 to -32	-31 to -29	1	2	4	8± 1	15 ±2	29± 3	91± 7	181 ±15	Phone call^
	V 1	V2	V3	V4	V5	V6	V7	V8	V9	V10	
Informed consent	x										
Demographics, medical history	x										
Interim medical history		x	x	x	x	x	x	x	x	x	x
Medications	x	x	x	x	x	x	x	x	x	x	x
Targeted physical exam	(x)	(x)	(x)	(x)	(x)	(x)	(x)	(x)	(x)	(x)	
Vital signs	(x)	(x)	(x)	(x)	(x)	(x)	(x)	(x)	(x)	(x)	
Blood draw for screening	x										
Stool Sample collection		x	x					x			
Pregnancy test (if applicable)	x		x	(x)	(x)	(x)	(x)	(x)	(x)	(x)	
Vaccination			x								
Statin therapy*		x	x	x	x	x	x	x			
Memory Aid			x	x	x						
Blood draw for immunological assays	x	x	x	x	x	x	x	x	x	x	
Clinical labs for statin therapy	x		x					x			
Adverse events		x	x	x	x	x	x	x			x
Serious adverse events		x	x	x	x	x	x	x	x	x	

Conducting a visit outside window is allowed at investigator discretion

Parentheses indicate a given procedure will be conducted if relevant for the visit: vital signs and pregnancy testing if applicable will be on the day of screening, prior to statin therapy initiation and prior to vaccination.

*Each participant receiving statin therapy will have clinical labs drawn. The tests conducted will be: Lipid profile, Creatinine Phosphokinase, Liver function tests, CRP. These tests will be valid for 30 days.

[^]phone call is completed 15 days after initiation of statin therapy.

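### Section 18.1 names renal impairment and hypothyroidism as raising myopathy risk, but entry screens the first by history alone and the second by no named criterion or test

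*Combined protocol and SAP*

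**What the plan says.** Section 18.1, among the rarer and more serious risks of atorvastatin, states: "Myopathy and rhabdomyolysis: risk increased with renal impairment, age>65 and hypothyroidism".

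Section 11 addresses these factors as follows.

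- **Age.** Participants must be 18 to 50.
- **Kidney, all participants.** Exclusion 4 covers "Chronic clinically significant medical problems that could be considered active or unstable", which it explains as a diagnosis or a change of medication within the past 3 months. One of its non-exhaustive examples is "Severe kidney disease".
- **Kidney, statin arm.** Item 2 of the additional list excludes "History of renal or hepatic impairment".
- **Laboratory limits, statin arm.** Item 3, headed "Safety lab results showing", sets limits for CPK, AST, ALT and LDL only.
- **Thyroid.** No criterion names it.

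The Appendix A footnote defines the clinical labs: "The tests conducted will be: Lipid profile, Creatinine Phosphokinase, Liver function tests, CRP". The second item is CPK, a muscle enzyme, and not serum creatinine. At the screening visit, Section 6.1.2 provides for "Recording of demographic information and review of medical history including recent influenza infection", with current medication use and baseline clinical labs. It does not mention thyroid disease or kidney function.

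**The concern.** By making renal impairment a statin-arm exclusion, the sponsor already treats it as a reason not to give the drug. Yet the plan has no listed measurement that would show whether a volunteer meets that exclusion, although it has one for the liver. For hypothyroidism, the plan names the risk and then does not say what is to be done about it at entry.

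The stake is participant safety. These are healthy adults with no stated lipid indication: LDL of 160 mg/dL or more is excluded in the statin arm, and Section 19 lists benefit from the vaccine only. An avoidable muscle event would have no offsetting benefit from the statin. Entry screening also carries much of the protection, because the first scheduled CPK on treatment comes late in the pre-vaccination period.

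**Working it through.** The plan states no figure to reproduce on this point. The check sets each factor named in Section 18.1 against the entry criteria and the lab panel.

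| Factor in 18.1 | Entry criterion (Section 11) | Test in listed panel (Appendix A) | Covered? |
|---|---|---|---|
| Age over 65 | Age 18-50 | Not needed | Fully |
| Renal impairment | History (statin list, item 2); severe disease (item 4e) | None | Only if already known |
| Hypothyroidism | None named; item 4 if judged active or unstable | None | Only in part |

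For comparison, hepatic impairment stands in the same item 2 and is backed by AST and ALT limits of 1.5 times ULN in item 3.

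**Who can pass the written criteria.** Barring another exclusion that happens to apply:

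1. A volunteer with reduced kidney function that has never been recognised has no history to report, so item 2 and item 4e are not met. The panel does not measure kidney function, so item 3 cannot catch it.
2. A volunteer with known hypothyroidism, diagnosed more than 3 months ago and with no change in medication in that time, does not meet the explanation of active or unstable in item 4.
3. A volunteer with undiagnosed hypothyroidism has nothing to report at the history review, and no thyroid test is listed.

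**When a muscle problem would next be looked for.** Appendix A schedules the clinical labs at V1, V3 (Day 1) and V8 (Day 29). Statin starts at V2 (Day -31 to -29). The first scheduled CPK on treatment is therefore at Day 1, about four weeks after the start. Between the two there is one scheduled contact, the phone call 15 days after initiation, which asks about compliance and complications. It involves no blood test unless the participant is called in.

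**Size.** The only event rate for serious muscle injury in the documents is the general statin figure of under 0.1% in Section 18.1. Applied to the statin arm, the expected count is under 30 x 0.001 = 0.03. That figure is not specific to people with either factor. The documents give neither the prevalence of the two conditions nor the increase in risk they carry, so the added expected count cannot be derived.

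**The case against.** **Section 18.1 is a risk list, not a promise to exclude.** This stands. There is no direct contradiction between 18.1 and Section 11. The point is that the plan names two factors and does not carry them through to entry.

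**Some cases would be caught.** This also stands. Any known renal impairment is excluded from the statin arm, whatever its grade. Item 4 is open-ended, history and medications are reviewed at V1, and eligibility is re-verified at V2. A reader might infer that hypothyroidism goes wholly unchecked; that is too strong. The gap is limited to unrecognised renal impairment and to stable or undiagnosed hypothyroidism. Appendix A also has a separate V1 screening blood draw whose contents are not itemised, so a renal test cannot be ruled out, but none is listed.

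**Other safeguards address muscle harm.** CPK of 1.5 times ULN or more bars entry to the statin arm, interacting drugs are excluded, labs may be repeated at the investigator's discretion, and Section 17 sets halting rules for CPK and symptoms. These limit the consequences but do not identify either risk factor.

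**A threat to the trial's continuation is not supported.** A reader might link this gap to Section 22.4, where triggers include one necrotizing autoimmune myopathy and "2 cases of severe myalgia". Section 18.1 attaches the two factors to myopathy and rhabdomyolysis only. It lists immune-mediated necrotizing myopathy and myalgia separately, without them. The triggers also suspend procedures pending review and do not end the study. Nor does an early departure necessarily shrink the arm of 30, since Sections 16 and 22.4 allow early terminations, up to about Day 8, to be replaced.

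**Assumed prevalences do not measure harm.** With n = 30 and an assumed prevalence p, the chance of enrolling at least one affected person is 1 - (1 - p)^30: 14% at 0.5%, 26% at 1%, 45% at 2% and 71% at 4%. These values of p are assumptions without a source in the documents, and the result is a chance of enrolment, ignoring the other exclusions. It shows only that an affected participant is plausible.

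**Conclusion.** The point holds as a gap between the plan's own risk statement and its entry screening. Of the three factors named in Section 18.1, one is fully closed. One is closed only where already known, and one is addressed only through a general clause that misses stable and undiagnosed disease. The conclusion rests on reading the Appendix A footnote as the full clinical panel, which is the natural reading.

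The added risk cannot be quantified from the documents and is probably small in absolute terms. No effect on the primary comparison and no link to the stopping triggers is claimed. It is worth correcting because the participants have no stated need for the statin, and because making the existing renal exclusion checkable costs very little.

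**What to change.** Reconcile Section 18.1, Section 11 and the Appendix A panel before any statin is dispensed.

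1. Make the existing renal exclusion verifiable. Add a renal function measure, for example serum creatinine, to the V1 clinical labs in Section 6.1.2 and the Appendix A footnote, on the draw already taken. Any limit is for the investigator to set. If the unitemised V1 screening draw already includes such a test, list it.
2. Have the investigator state in Section 11 or Section 18.1 how hypothyroidism is handled at entry, with the reason. No clinical rule is proposed here.

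The cost is one inexpensive analyte on an existing draw, a short statement, and possibly a few extra screen failures among the 150 people Section 14 plans to screen.

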18.1 Risks of Investigational Products/Interventions

Atorvastatin therapy

Atorvastatin is an FDA-approved lipid lowering drug that is widely used. In some cases, this statin may be associated with the following risks:

- Diarrhea, nasopharyngitis, arthralgia in 4-14%

- Insomnia in 3%
- Nausea and dyspepsia in 4-6%
- Increased transaminases in 2-3%
- Muscle spasms, myalgia, musculoskeletal pain in 3 to 8%

Treatment with Atorvastatin may also be rarely linked to more serious risks such as:

- Hypersensitivity or severe allergic reaction including anaphylaxis, angioneurotic edema, erythema multiforme, Stevens-Johnson syndrome, and toxic epidermal necrolysis
- Acute liver failure or decompensated cirrhosis
- Nonserious and reversible cognitive side effects
- Fatal and nonfatal hepatic failure
- Increases in HbA1c and fasting serum glucose levels
- Myopathy and rhabdomyolysis: risk increased with renal impairment, age>65 and hypothyroidism
- Increases in serum transaminases. These changes occurred following the start of statin therapy, were not accompanied by other symptoms, and reversible after drug discontinuation
- Persistent increases to more than three times the ULN in serum transaminases have occurred in approximately 0.7% of patients
- Immune-mediated necrotizing myopathy: characterized by muscle biopsy showing necrotizing myopathy without significant inflammation, improvement with immunosuppressive agents, proximal muscle weakness, and elevated serum creatine kinase, which persist despite discontinuation of statin treatment

A scientific statement from the American Heart Association²² supports the safety of statin therapy including in people at low risk for cardiovascular disease, noting the risk of statin-induced serious muscle injury is <0.1% and risk of serious hepatotoxicity is <0.01%. Current product labels do not include the need for routine monitoring of liver enzymes if these are normal prior to initiating statin therapy. For safety, liver enzymes and creatine phosphokinase (CPK) will be monitored on a regular basis during the study.

Seasonal influenza vaccine

The potential harms of receiving the influenza vaccine include, but are not limited to: pain and redness at the injection site, muscle aches, fatigue, and headache. These reactions occur in 10-25% of adults who receive influenza vaccine. Serious adverse reactions including anaphylaxis and Guillain-Barré syndrome are possible, but rare. Potential participants with a history of severe allergic reaction to any component of the vaccine or Guillain-Barré syndrome after previous influenza vaccination will not be enrolled. For further details, see the attached package insert.

18.2 Risks of study procedures

Blood draws

The risks of blood sample collection include a transient feeling of discomfort and may result in a vasovagal reaction. This risk is controlled by having the participant lie down prior to collection, if needed. A bruise might form at the site of the blood draw, and this can be avoided by maintaining pressure to this site following the blood draw. The sites of blood draw are potential sites of infection, but this risk is made very unlikely by the use of sterile technique.

18.3 Risk of Concomitant Medications, Prophylactic Medications and Rescue Medications

While we do not expect to use any additional medication, in case of anaphylactic or hypersensitivity reactions, we have readily available epinephrine (1:1000) and diphenhydramine injections. The use of epinephrine injection may cause side effects such as high blood pressure, arrhythmia, lightheadedness, nervousness, restlessness, tremor, shortness of breath, and diaphoresis; however, the frequency of these side effects is not determined. Diphenhydramine injection may also be necessary to treat potential allergic reactions, and its use may cause low blood pressure, arrhythmia, confusion, dizziness, sedation, restlessness, diarrhea, nausea, and urinary retention, but the frequency of these side effects is also unknown.

When facing a medical emergency, the clinic staff will follow the institutional SOP by calling 911 first (Hope Clinic). If needed, the participant will be transferred to the Emory University Hospital or Emory Decatur Hospital Emergency Department for further care.

Participants are allowed to use acetaminophen or other symptomatic treatment if they experience a moderate to severe local or systemic side effect after vaccine administration.

19. Potential Benefits to Participants

The participants will be administered the influenza vaccine that has been approved by the FDA, which may potentially provide them with protection against influenza viruses. The United States Advisory Committee on Immunization Practices (ACIP) recommends the influenza vaccine for individuals aged 6 months and above, as it is known to be effective in preventing influenza virus infection.

20. Compensation to Participants

As compensation for expenses/travel and time, participants will receive \$75 for each visit that involves a blood draw, \$100 for the statin initiation visit, and \$125 for the vaccination visit. Any unscheduled visit will be compensated at \$50. Phone visits are compensated \$20 per call. Compensation is provided in the form of a gift debit/credit card (ClinCard). If a participant completes all visits, total compensation will range from \$725-\$845 depending on the arm they are randomized to. In the event gift debit/credit cards (ClinCard) are unavailable, gift card reimbursement may be used instead.

21. Data Management and Confidentiality

21.1 Steps taken to secure data

All faculty and staff at the Hope Clinic receive HIPAA, human participants, and EHSO training as part of their onboarding and continuing training. Each participant will be assigned a unique study participant identification number (PTID) and these numbers rather than names will be used to collect and store participant information, including omics data.

Investigators and study personnel will keep accurate records to ensure that the conduct of the study is fully documented. Clinical data from this study, including participant birthdate and demographics, will be associated with the PTID, maintained on a HIPAA compliant clinical management database and a HIPAA compliant RedCap database and/ or password protected Excel file, respectively at Hope Clinic accessible to investigators and study personnel only. Hard copy clinical data forms, for example source or protocol-specific CRFs, associated with the PTID will be stored at Hope Clinic in a locked file cabinet and accessible to investigators and clinical staff only. A file linking the participant PII (i.e., their name and contact information) to their PTID will be maintained at the Hope Clinic in a separate locked file cabinet and HIPAA compliant clinical management database accessible to investigators and clinical staff only. Study personnel will only send documents containing personal PII via fax or encrypted email in accordance with HIPAA regulations (e.g., to send/receive safety lab data and medical records request to/from primary care provider).

